3.3. Prohibited Concomitant Medications and Treatments

Use of the following therapies is prohibited during the study:

- Any concomitant therapy intended for the treatment of subject's current cancer, whether health authority-approved or experimental, including (but not limited to) the following: chemotherapy, hormonal therapy for cancer treatment, immunotherapy, radiotherapy, investigational agents, or herbal therapy.
- Immunostimulatory agents or immunotherapy not specified in the protocol.
- Immunosuppressive medications, including but not limited to cyclophosphamide, azathioprine, methotrexate, thalidomide, and immunosuppressive doses of corticosteroids (i.e. >10 mg daily prednisone equivalent). (These agents may be administered at the discretion of the treating physician in an emergency or after consultation with the Medical Monitor).
- Surgical resection except for palliative surgical resection.

3.4. Screen Failures

Screen failures are defined as subjects who consent to participate in the clinical study but are not subsequently enrolled. A minimal set of screen failure information is required to ensure transparent reporting of screen failure subjects to meet the Consolidated Standards of Reporting Trials (CONSORT) publishing requirements and to respond to queries from regulatory authorities. Minimal information includes demography, screen failure details, eligibility criteria, and any serious adverse events (SAE) related to protocol required procedures. Retesting of individual laboratory parameters to determine eligibility is permitted if the values are:

- Not consistent with life or the subject's current medical status.
- Aberrant due to a spoiled sample. e.g., hemolyzed hematology sample.

Individuals who do not meet the criteria for participation in this study (screen failure) may be rescreened, if their medical status changes and they subsequently qualify for the study or there is an amendment to the protocol which allows participation. Rescreened subjects should not be assigned the same subject number as for the initial screening.

Screen failures may be rescreened only once, after approval from the sponsor. If rescreening is less than 28 days prior to first study drug administration (Cycle 1, Day 1), the following assessments may be used for rescreening:

- Previously submitted CT and MRI scans with acquisition date \leq 28 days prior to Cycle 1 Day 1. Scans that exceed the 28-day window may be used for enrollment with sponsor approval.
- Previously submitted tumor biopsy sample
- Screening laboratory assessments that meet protocol-defined timelines as indicated in [Table 3](#)

If rescreening is more than 28 days after the initial screen failure, the subject must be re-consented, and all eligibility criteria must be re-assessed with repeat screening assessments as per protocol specified guidelines with the following exceptions:

- Scans that exceed the 28-day window may be used for enrollment with sponsor approval.
- Previously submitted tumor biopsy sample

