3. STUDY POPULATION

Prospective approval of protocol deviations to recruitment and enrollment criteria, also known as protocol waivers or exemptions, is not permitted.

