9.3. Statistical Analyses

All statistical analyses for this study will be undertaken by a contract research organization under the supervision of sponsor personnel. Any data analysis carried out independently by the investigator should be submitted to the sponsor prior to publication or presentation.

All data will be listed. All trial endpoints will be described using summary statistics. Data will be summarized using descriptive statistics for continuous data (safety laboratory data, pharmacodynamic and relevant biomarker data), and contingency tables for categorical data

(demographics and other baseline characteristics, efficacy measurements, safety measurements and all relevant PK measurements.

For statistical analyses and summaries, baseline is defined as the available data from the last recorded measurement prior to first administration of study drug.

Details of statistical analysis and data reporting will be provided in a SAP document finalized prior to database lock. Additional analyses may be added in the SAP and tables, listings and figures shells will also be provided.

The SAP will be developed and finalized before database lock and will describe the selection of subjects to be included in the analyses, and procedures for accounting for missing, unused, and spurious data. Below is a summary of planned statistical analyses of the study endpoints.

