- Lesions that meet the criteria for radiographically defined simple cysts should not be considered as malignant lesions (neither measurable nor non-measurable) since they are, by definition, simple cysts.
- 'Cystic lesions' thought to represent cystic metastases can be considered as measurable lesions, if they meet the definition of measurability described above. However, if noncystic lesions are present in the same subject, these are preferred for selection as target lesions.

Lesions with prior local treatment:

- Tumor lesions situated in a previously irradiated area, or in an area subjected to other loco-regional therapy, are usually not considered measurable unless there has been demonstrated progression in the lesion. Study protocols should detail the conditions under which such lesions would be considered measurable.

Measurement of Lesions

- All measurements should be taken and recorded in metric notation, using calipers if clinically assessed. All baseline evaluations should be performed as closely as possible to the beginning of treatment and never more than 28 days before the beginning of the treatment.

Methods of Measurement

- The same method of assessment and the same technique should be used to characterize each identified and reported lesion at baseline and at each subsequent response assessment. Imaging based evaluation should always be done rather than clinical examination unless the lesion(s) being followed cannot be imaged but are assessable by clinical examination.
- For the case of skin lesions, documentation by color photography, including a ruler to estimate the size of the lesion, is recommended.
- CT is currently the best currently available and reproducible method to measure target lesions selected for response assessment. The CT scan slice thickness should be 5 mm or less. When the CT scans have a slice thickness that is greater than 5 mm, the minimum size for a measurable lesion should be twice the slice thickness. MRI is also acceptable.
- Lesions on chest X-ray are acceptable as measurable lesions when they are clearly defined and surrounded by aerated lung. However, CT is preferable.
- Ultrasound (US) should not be used to measure tumor lesions. The utilization of endoscopy and laparoscopy for objective tumor evaluations not advised.
- Fluorodeoxyglucose positron emission tomography (FDG-PET) can be used to determine a new lesion if the lesion was absent at baseline on FDG-PET

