Complete Response (CR):	Disappearance of all target lesions. Any pathological lymph node (whether target or nontarget) must have reduction in short axis to <10 mm
Partial Response (PR):	At least a 30% decrease in the sum of the diameters of target lesions, taking as reference the baseline sum diameters
Progressive Disease (PD):	At least a 20% increase in the sum of the diameters of target lesions, taking as reference the smallest sum on study (this includes the baseline sum if that is the smallest on study). In addition to the relative increase of 20%, the sum must also demonstrate an absolute increase of at least 5 mm. The appearance of one or more new lesions is also considered progression.

Evaluation of Non-Target Lesions

Complete Response (CR):	Disappearance of all non-target lesions and normalization of tumor marker level. All lymph nodes must be non-pathological in size (ie, <10 mm short axis).
Non-CR/Non-PD	Persistence of one or more non-target lesion(s) and/or maintenance of tumor marker level above the normal limits
Progressive Disease (PD):	Unequivocal progression of the existing non-target lesions. The appearance of one or more new lesions is also considered progressive disease.

Although a clear progression of “non target” lesions only is exceptional, in such circumstances, the opinion of the investigator should prevail.

Evaluation of Overall Response

Table 6 Evaluation of Overall Response

Target lesions	Non-Target lesions	New Lesions	Overall response
CR	CR	No	CR
CR	Non-CR/Non-PD	No	PR
CR	Not evaluated	No	PR
PR	Non-PD or not all evaluated	No	PR
SD	Non-PD or not all evaluated	No	SD
Not all evaluated	Non-PD	No	NE
PD	Any	Yes or No	PD
Any	PD	Yes or No	PD
Any	Any	Yes	PD

- Subjects with a global deterioration of health status requiring discontinuation of treatment without objective evidence of disease progression at that time should be classified as having “symptomatic deterioration”. Every effort should be made to document the objective progression even after discontinuation of treatment.

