Written description	
This is an open-label, multicenter, Phase 1b/2 basket study designed to evaluate the efficacy, safety, tolerability, pharmacokinetics (PK), and pharmacodynamics (PD) of etigilimab in combination with nivolumab in subjects with recurrent, locally advanced and/or metastatic solid tumors who are not candidates for available, curative standard of care therapies. In cohorts enrolling tumor types for whom anti-PD-1 antibody therapy is approved treatment for recurrent, locally advanced or metastatic disease, subjects may be enrolled prior to treatment with anti-PD-1 antibody therapy. Subjects will be assigned to receive etigilimab (█ mg every 2 weeks for subjects ≥50 kg, █ mg/kg dose every 2 weeks for subjects <50 kg) in combination with nivolumab (240 mg every 2 weeks) and will continue until protocol-defined discontinuation criteria are met. Cohorts will be enrolled at the discretion of the sponsor. Selected cohorts will be open for the first 20 subjects enrolled without increasing the total number of subjects proposed for the trial. During the conduct of this open label study an Independent Data Monitoring Committee (IDMC) will be established and will review study data on an ongoing basis.

Screening period	
All screening tests must be performed within 28 days preceding Day 1 (defined as the first day of study drug administration), unless otherwise indicated. Results of standard-of-care tests or examinations performed prior to obtaining informed consent and within the screening window may be used and do not have to be repeated if they meet protocol specifications. The screening period will include medical history and demographic data collection, physical examination including vital signs, laboratory assessments including hematology, serum chemistry and urinalysis, electrocardiogram (ECG), collection of blood for immunogenicity, PK, and

	tumor marker assessments, and collection of blood and formalin-fixed paraffin-embedded (FFPE) or fresh tumor samples for biomarker assessments.		
Treatment period	Subjects will be assigned to receive etigilimab (■ mg every 2 weeks for subjects ≥ 50 kg, ■ mg/kg dose every 2 weeks for subjects < 50 kg) in combination with nivolumab (240 mg every 2 weeks) and will continue until protocol-defined discontinuation criteria are met.		

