10.8. Efficacy Analysis

10.8.1. Primary Endpoint

10.8.1.1. Objective Response Rate

Up to 5 target lesions are identified and measured at baseline, along with any non-target lesions. At each tumour assessment response is then recorded based on the target lesions according to the RECIST v1.1 criteria. Target lesions and non-target lesions are assigned a 'response' (as per Table 3 and Table 4). These are then combined to give an evaluation of overall response as per Table 5.

Table 3: Evaluation of Target Lesions

Complete Response (CR):	Disappearance of all target lesions. Any pathological lymph node (whether target or nontarget) must have reduction in short axis to <10 mm
Partial Response (PR):	At least a 30% decrease in the sum of the diameters of target lesions, taking as reference the baseline sum diameters
Progressive Disease (PD):	At least a 20% increase in the sum of the diameters of target lesions, taking as reference the smallest sum on study (this includes the baseline sum if that is the smallest on study). In addition to the relative increase of 20%, the sum must also demonstrate an absolute increase of at least 5 mm. The appearance of one or more new lesions is also considered progression.

Table 4: Evaluation of Non-Target Lesions

Complete Response (CR):	Disappearance of all non-target lesions and normalization of tumor marker level. All lymph nodes must be non-pathological in size (ie, <10 mm short axis).
Non-CR/Non-PD	Persistence of one or more non-target lesion(s) and/or maintenance of tumor marker level above the normal limits
Progressive Disease (PD):	Unequivocal progression of the existing non-target lesions. The appearance of one or more new lesions is also considered progressive disease.

Although a clear progression of “non target” lesions only is exceptional, in such circumstances, the opinion of the investigator should prevail.

Table 5: Evaluation of Overall Response

Target lesions	Non-Target lesions	New Lesions	Overall response
CR	CR	No	CR
CR	Non-CR/Non-PD	No	PR
CR	Not evaluated	No	PR
PR	Non-PD or not all evaluated	No	PR
SD	Non-PD or not all evaluated	No	SD
Not all evaluated	Non-PD	No	NE
PD	Any	Yes or No	PD
Any	PD	Yes or No	PD
Any	Any	Yes	PD

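### Section 3.4 lets rescreened subjects enrol on tumour scans older than 28 days with no maximum age, against Appendix 7, so size change before treatment can enter the primary response endpoint

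*Protocol*

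**What the plan says.** Protocol Section 3.4 covers screen failures who return: "Screen failures may be rescreened only once, after approval from the sponsor". It has two branches, and both contain the same allowance: "Scans that exceed the 28-day window may be used for enrollment with sponsor approval". The first branch is for rescreening close to first dose and also lets scans still within 28 days be reused. The second is for rescreening more than 28 days after the screen failure. There the allowance is listed as an exception to repeating the screening assessments. Neither branch states a maximum scan age.

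Appendix 7 (Measurement of Lesions) says baseline evaluations are to be as close as possible to the start of treatment and "never more than 28 days before the beginning of the treatment". The synopsis says "All screening tests must be performed within 28 days preceding Day 1", subject to a clause for cases where something else is indicated. In the schedule (Section 8.1) the screening window opens at Day -28. It has one tumour assessment before treatment, at screening, and the next at Day 57.

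For analysis, Protocol 9.3 says "baseline is defined as the available data from the last recorded measurement prior to first administration of study drug". SAP 10.1.1 leaves the efficacy baseline to the endpoint sections, and SAP 10.8.1.1 says only "Up to 5 target lesions are identified and measured at baseline, along with any non-target lesions", with no scan window. PR is defined as "At least a 30% decrease in the sum of the diameters of target lesions, taking as reference the baseline sum diameters". PD is measured from the smallest sum on study, which can be the baseline sum.

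**The concern.** The two protocol texts cannot both hold for the scan that serves as baseline. In the second branch of 3.4, a scan from the original screening is out of window by construction, because rescreening itself starts more than 28 days after the failure. If the rescreening period then runs to 28 days, the scan is more than 28 + 28 = 56 days old at first dose, plus the time between the scan and the screen failure.

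The baseline sum is the denominator for PR and may be the reference for PD. With an old scan, the recorded change mixes what happened before the first dose with what happened on treatment. In a single-arm study with confirmed ORR as the primary endpoint there is no control group in which this would cancel. The same reference feeds DCR, duration of stable disease and PFS.

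**Working it through.** **Step 1. Does the old scan become the reference?** Section 3.4 permits it for enrolment and, in the second branch, removes the need to repeat it. Section 8.1 requires no further tumour assessment until Day 57. Protocol 9.3 takes the last measurement before first dose. SAP 10.8.1.1 sets no age limit. Following these texts, the approved old scan is the only measurement available as baseline.

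**Step 2. Effect on one subject.** Let S be the sum of diameters on the old scan, and S(1+g) the sum at first dose. PR needs a sum of at most 0.70·S.
- Shrinkage from the first-dose size needed for PR: 1 − 0.70/(1+g).
- Recorded change for a true 30% shrinkage: 0.70(1+g) − 1.
- Growth on treatment that meets the 20% PD rule when the old scan is the smallest sum: 1.20/(1+g) − 1. The 5 mm absolute rule also applies.

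The documents give no growth rates, so g is an assumption.

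| g | Shrinkage needed for PR | True 30% shrinkage recorded as | Growth meeting the 20% rule |
|---|---|---|---|
| 0 | 30.0% | 30.0% | 20.0% |
| 5% | 33.3% | 26.5% (SD) | 14.3% |
| 10% | 36.4% | 23.0% (SD) | 9.1% |
| 20% | 41.7% | 16.0% (SD) | 0% |

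As a check on the range: with assumed volume doubling times of 60 to 180 days, diameter growth over d days is 2^(d/(3 × doubling time)) − 1. That is 4% to 11% over 28 days and 7% to 24% over 56 days.

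**Step 3. The opposite direction.** Section 3.1 allows palliative radiotherapy completed at least 2 weeks before first dose. Section 3.2 bars prior systemic therapy only for 28 days or 5 half-lives, whichever is shorter. Either can fall after a scan more than 28 days old. If the sum shrinks by an assumed h before first dose, the on-treatment shrinkage needed for PR is 1 − 0.70/(1−h): 26.3%, 22.2% and 12.5% for h = 5%, 10% and 20%.

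**Step 4. How many subjects.** Section 2.1 plans about 135 screened and 125 enrolled, so 135 − 125 = 10 screen failures. If all were rescreened and enrolled on old scans, the share would be 10/125 = 8%. The protocol does not count rescreens, so this is a rough ceiling.

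**Step 5. Effect on the design.** The stated Simon figures come from the exact binomial sum over stage 1 (10 subjects) and stage 2 (19 subjects).
- Type 1 (at least 1 of 10, then 4 of 29): type I error 0.0468, power 80.11%. Both reproduce.
- Type 2 (at least 2 of 10, then 6 of 29): type I error 0.0471, power 80.51%. Both reproduce.

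Now replace the alternative rate p1 by p1(1 − s·l), where s is the share of subjects on old scans and l the share of their responses lost (both assumed).

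| s | l | Type 1 power | Type 2 power |
|---|---|---|---|
| 8% | 10% | 79.6% | 79.9% |
| 8% | 50% | 77.5% | 77.4% |
| 8% | 100% | 74.5% | 73.9% |
| 20% (one cohort) | 50% | 73.0% | 72.0% |

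One reclassified subject moves ORR by 1/10 = 10 percentage points in a cohort of 10, and by 1/29 = 3.4 points in a cohort of 29.

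**The case against.** The strongest objection is that Section 3.4 speaks of enrolment, not baseline. An old scan could support eligibility while Appendix 7 still governs the RECIST baseline. That reading is possible, but no text asks for a second scan and the second branch excuses the repeat. A site following 3.4 and the schedule would have nothing else to use.

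Several stronger readings are tempting and are not supported:
- **That the allowance breaches the waiver ban.** Section 3 says that prospective approval of deviations from enrolment criteria, "also known as protocol waivers or exemptions, is not permitted". An exception written into the protocol is not clearly a deviation from it, no criterion in 3.1 or 3.2 sets a scan age, and the synopsis window yields where another section says otherwise.
- **That ORR is biased downwards.** This would need every tumour to be growing before first dose. Not every cohort requires progression: the sarcoma criteria do not, and Cohort B admits first-line HNSCC. Step 3 shows the reverse direction.
- **That scan age is hidden.** Listing 16.2.6.2.1 shows the assessment date and study day for each target lesion. What is missing is any table or analysis that uses them.
- **That stage 1 decisions are at risk.** SAP 6.3 reports that the futility evaluation took place for the cervical and uveal cohorts, that both were approved to proceed, and that the other cohorts did not need it before the study was terminated. SAP 10.1.3 plans no hypothesis test.

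The point about scope stands: few subjects can be affected, and not every rescreened subject would be on an old scan.

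**Conclusion.** The contradiction between Section 3.4 and Appendix 7 is real, and the allowance has no upper limit. Its consequence, that change before treatment is attributed to treatment, follows from the schedule and the baseline definition; it is not stated outright. The direction for any one subject depends on whether the tumour grew or shrank between scan and first dose.

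The expected overall effect is small. Even if all 10 planned screen failures were enrolled on old scans, losing 10% of their responses costs 0.5 to 0.6 percentage points of power, and losing all of them costs 5.6 to 6.6 points. These figures describe the design only, since no test is now planned. What remains at stake is the reported ORR and its interval in cohorts of 10 to 29 or smaller, where one subject is visible. The growth rates, the shrinkage rates, the share on old scans and the share of responses lost are all assumptions.

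**What to change.** **In the SAP (main remedy, as the study has been terminated).** Use the assessment dates in Listing 16.2.6.2.1 to identify subjects whose baseline scan was more than 28 days before Cycle 1 Day 1. Add a footnote to Table 14.2.1 giving, by cohort, their number and the ORR with Clopper-Pearson interval excluding them, as a sensitivity analysis. If there are none, say so. Do not class sponsor-approved use under 3.4 as an important protocol deviation by default, because the protocol permits it.

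**In any continued or reused protocol.** Reconcile Section 3.4 with Appendix 7 so that the RECIST baseline CT or MRI falls within 28 days before Cycle 1 Day 1, including after rescreening. A scan still within 28 days stays reusable.

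**Cost.** One small analysis on dates already collected. A protocol change would need an amendment with ethics approval, and a few rescreened subjects would have the in-window scan that the schedule already calls for.

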4. TREATMENTS

Study treatment is defined as any investigational treatment(s), marketed product(s), placebo, or medical device(s) intended to be administered to a study subject according to the study protocol.

4.1. Treatments Administered

Study Treatment Name:	Etigilimab	Nivolumab
Dosage formulation:	█ mg/mL in a █-mL single-use glass vial filled to █ mL to deliver a total of █ mg per vial	40 mg/4 mL (10 mg/mL), 100 mg/10 mL (10 mg/mL), or 240 mg (24 mL) solution in a single-use vial
Unit dose strength(s) /Dosage level(s):	█ mg if subject is \geq 50 kg █ mg/kg if subject is $<$ 50 kg	240 mg
Route of Administration:	IV	IV
Dosing instructions:	The initial dose of etigilimab will be delivered on Day 1 over 90 ± 10 minutes followed by a 90-minute observation period. If the 90-minute infusion is tolerated without infusion-associated adverse events, the second infusion may be delivered over 60 ± 10 minutes followed by a 60-minute observation period. If the 60-minute infusion is well tolerated, all subsequent infusions may be delivered over 30 ± 10 minutes followed by a 30-minute observation period per investigator's discretion. Etigilimab will be delivered prior to nivolumab. The etigilimab observation period will need to be completed before dosing nivolumab. If the subject is $<$ 50 kg, the dose will be based on the subject's weight at each treatment visit.	Vials will be diluted with 0.9% sodium chloride injection, USP or 5% dextrose injection, USP prior to use. It is administered over $30 + 10$ minutes (never $<$ 30 minutes) through an intravenous line containing as sterile, non-pyrogenic, low protein binding in-line filter (pore size of 0.2 micrometer to 1.2 micrometer). The initial dose of nivolumab will be delivered on Day 3.
Packaging and Labeling:	Study Treatment will be provided as 10 vials in a carton. Each vial and carton will be labeled as required per country requirement.	Commercial stock will be utilized.

